We plan to enroll 67 children with hematologic malignancies (including acute myeloid leukemia, acute lymphoblastic leukemia, juvenile myelomonocytic leukemia, and myelodysplastic syndrome) at the time of HSCT at three institutions (including UCSF, All Children's Hospital, St. Petersburg, FL, and Lucile Packard Children's Hospital, Palo Alto, CA). Patients will be enrolled on the study by day +28, prior to withdrawal of immunosuppression or administration of donor lymphocyte infusion (DLI). They will have donor chimerism and minimal residual disease (MRD) testing from the peripheral blood (PB) and bone marrow (BM) on day $+28 \pm 7$ (as per standard of care). Based on risk assessment, patients will receive one cycle of low-dose azacitidine ($40\text{mg}/\text{m}^2$ IV/SC daily $\times 4$ days) alone as immunosuppression is tapered. After tapering immunosuppression, chimerism will be repeated and patients will receive up to 6 additional cycles of low-dose azacitidine. For patients who meet at high risk for relapse, azacitidine will be combined with escalating doses of DLI for a maximum of 7 cycles in total. Risk and safety assessments, including routine laboratory parameters, donor chimerism, minimal residual disease, and GHVD activity will be assessed following each cycle.

The primary outcome measures will be indicators of relapse risk and safety / toxicity. Patients will be followed for relapse as well as incidence of severe drug toxicities and acute and chronic GVHD until 2 years post-transplant. The study will be considered successful if the rate of relapse at 2 years is $<25\%$, and the incidence of Grade IV GVHD and severe drug toxicity are $<20\%$. Correlative studies will include the effect of azacitidine on T cell immune reconstitution, as well as prospective minimal residual disease estimation by gene expression / mutation panels in patients with AML.

Study Schema

Standard Risk:

- Active Grade I GVHD, OR
- Any history of >Grade II GVHD, OR
- Full Donor Chimerism AND Pre-HSCT MRD-neg AND Post-HSCT MRD-neg

High Risk:

- No GVHD or resolved Grade I GVHD, AND
- Mixed chimerism OR Pre-Tx MRD(+) OR Post-Tx MRD(+)

[figure not shown]

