8.4 Sample size

- 8.4.1 The sample size is estimated using Bayesian sequential monitoring design with toxicity and response outcomes as multiple endpoints(45). It is assumed that the rate of relapse in pediatric acute leukemia post-transplant would be 40% (as shown in our pilot study), azacitidine +/- DLI would reduce the 2-year relapse rate by approximately 40% to a rate of 25%. A sample size of 67 evaluable patients is required to provide 80% power at a one-sided significance level of 0.05 to test the hypothesis based on the relapse rate of H0: relapse rate > 40% (historically-controlled) versus Ha: relapse rate < 25% (treatment-targeted). The study will enroll patients until accrual of 67 patients is achieved.
- 8.4.2 Enrollment of 67 patients will be attainable with enrollment at multiple centers. Investigators from All Children's Hospital, Lucille Packard Children's Hospital have written letters of support expecting to enroll 30-40 patients over 2 years.

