8.7 Interim analysis and stopping rules for safety and efficacy

- 8.7.1 As a phase II study with 67 evaluable patients, the study is designed to have interim stopping rules based on the safety/toxicity evaluation (including death and incidence of severe GVHD). See Section 11.0 for reporting SAEs associated with study stopping rules.
- 8.7.2 The occurrence of any serious adverse events (SAEs) will be reported to the Coordinating Trial Center within 24 hours of learning about them, and within 10 days in writing. See Section 11.0 for SAE definitions and reporting requirements. A rate of SAEs of up to 20% is deemed acceptable in view of the potential benefit of the therapy. Accrual will stop if 3 patients with SAEs are observed in the first 3-6 patients undergoing the intervention, if 4 patients with SAEs are observed in the first 7-9 patients undergoing the intervention, or if 5 patients with SAEs are observed in the first 10-13 patients undergoing the intervention. The following table displays the minimum

number of SAEs for the study to be stopped at each accrual period and the probability of early stopping at the assumed SAE rate.

Patients on Study	4-6	7-9	10-13	14-17	18-21	22-27
Number of patients with SAE	≥3	≥4	≥5	≥6	≥7	≥8
15%SAE	1.2%- 4.2%	1.1%- 2.8%	0.9%- 2.7%	0.9%- 2.4%	0.9%- 2.0%	0.8%- 2.6%
20%SAE	2.6%- 8.2%	2.9%- 6.6%	2.6%- 6.9%	3.2%- 6.8%	3.5%- 6.6%	3.6%- 8.2%
25%SAE	4.7%- 13.2%	5.8%- 11.7%	5.8%- 12.6%	7.3%- 12.8%	8.2%- 12.7%	8.9%- 14.2%

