8.7.3 Stopping rules for interim toxicity and relapse futility

- Study data will be analyzed for relapse rates within 3 months for efficacy assessment. Such early futility assessment will be done when the first 14 patients have completed the 3-month follow-up in the study. If there are 9 or more relapses out of 14 patients during the futility assessment, enrollment will be stopped due to futility. Otherwise an additional 54 patients will be accrued for a total of 67 patients in the study. By the end of the study, if there are 32 or more relapses observed, further investigation will not proceed. In this study the rate of relapse in pediatric acute leukemia post-transplant is assumed to be 40% (as shown in our pilot study), azacitidine +/- DLI would reduce the 2-year relapse rate by approximately 40% to a rate of 25% and that the toxicity rate in pediatric acute leukemia post-transplant under azacitidine +/- DLI would be 20%. The stopping rules for toxicity and relapse rate under sequential design of multiple endpoints are shown below:
- For patients receiving DLI, a subset analysis of incidence of Grade III-IV aGVHD and mortality secondary to GVHD will be performed when a new patient is diagnosed with Grade III-IV GVHD or chronic GVHD.
 - Reported rates of grade III-IV acute GVHD following DLI range from 20-35%; GVHD-related mortality ranges from 5-15%.
 - If rates of Grade III-IV aGVHD or GVHD-related mortality in this study exceed published rates, enrollment and further DLI administration will be suspended while further safety analysis is performed.

Patients on Study	<14	15-21	22-28	29-35	36-42	43-49	50-56	57-63
Number of patients with SAE (Toxicity)	>8	≥10	≥13	≥16	≥18	≥21	≥23	≥26
Number of patients with relapse in 3 months	>9	≥13	≥16	≥19	≥23	≥26	≥29	≥32

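### The 8.7.3 toxicity limits match a reference rate near 30%, not the stated 20%; they conflict with 8.7.2 up to patient 27 and almost never stop the trial after it

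*Combined protocol and SAP*

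**What the plan says.** Three places give a 20% figure. Section 8.7.3 assumes that "the toxicity rate in pediatric acute leukemia post-transplant under azacitidine +/- DLI would be 20" per cent. Section 8.7.2 states: "A rate of SAEs of up to 20% is deemed acceptable in view of the potential benefit of the therapy". The protocol summary counts the study a success only if, among other things, the "incidence of Grade IV GVHD and severe drug toxicity are" below 20%.

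The 8.7.3 table has two rows.
- The row labelled "Number of patients with SAE (Toxicity)" stops at >8 for fewer than 14 patients, then at ≥10 (15–21), ≥13 (22–28), ≥16 (29–35), ≥18 (36–42), ≥21 (43–49), ≥23 (50–56) and ≥26 (57–63).
- The relapse row prints >9 in its first cell, while the text says: "If there are 9 or more relapses out of 14 patients during the futility assessment, enrollment will be stopped due to futility". It continues ≥13, 16, 19, 23, 26, 29, 32.

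Section 8.4.1 names a Bayesian sequential monitoring design and tests "H0: relapse rate > 40% (historically-controlled) versus Ha: relapse rate < 25% (treatment-targeted)". No prior, probability cut-off or stopping probability is given for 8.7.3.

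Section 8.7.2 has its own all-patient SAE rule. Accrual stops at 3 affected patients (text: first 3–6; table: 4–6), 4 (7–9), 5 (10–13), 6 (14–17), 7 (18–21) and 8 (22–27). It ends at patient 27. Section 7.1.2, the termination clause for toxicity and futility, cites only 8.7.3.

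**The concern.** A stopping limit should follow from the rate the protocol says it will tolerate. The last 8.7.3 limit does not stop the trial at 25 affected patients of 63. That is 39.7%, with an exact 95% interval of 27.6% to 52.8%, wholly above 20%. This comparison needs no assumption about prior or cut-off.

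Sections 8.7.2 and 8.7.3 also give different answers over the same patients, for example ≥7 at 18–21 against ≥10 at 15–21, and no section says which governs. After patient 27 only 8.7.3 supplies a numerical limit for all patients. At stake is whether the later part of a paediatric trial, up to 40 of 67 patients, has working toxicity monitoring.

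**Working it through.** **Inputs.** Limits and rates are from 8.7.2, 8.7.3 and 8.4.1. The prior and cut-off are inferred. The first toxicity cell (>8 below 14) is read as 8 at 14 patients, and the first relapse cell as 9 at 14, as in the text. Looks are at n = 14, 21, 28, 35, 42, 49, 56, 63.

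**1. Reproduce the relapse row.** With a flat Beta(1,1) prior and x events in n, the posterior is Beta(1+x, 1+n−x). The limit is the smallest x for which P(rate > reference) exceeds the cut-off. Reference 40%, cut-off 0.95 gives 9, 13, 16, 19, 23, 26, 29, 32, which is the printed row. Any cut-off from 0.9493 to 0.9574 gives the same row.

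**2. Apply the same rule to toxicity.**

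| Reference, cut-off | Limits at 14, 21, …, 63 |
|---|---|
| Printed | 8, 10, 13, 16, 18, 21, 23, 26 |
| 20%, 0.95 | 6, 8, 9, 11, 13, 15, 17, 18 |
| 30%, 0.95 | 8, 10, 13, 15, 18, 20, 23, 25 |
| 30%, 0.955 | 8, 10, 13, 16, 18, 21, 23, 26 |

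At 30% the printed row is reproduced for cut-offs from 0.9545 to 0.9613. That overlaps the relapse range, so one cut-off near 0.955 yields both rows. At 20% the row is not reproduced even at a cut-off of 0.999. Other weak priors, and cut-offs of 0.95–0.96, move each 20% limit by at most one patient. Across priors and cut-offs, references from 29% to about 33% can fit the printed row exactly.

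**3. Stopping probabilities.** These come from an exact binomial recursion, treating patients as independent with a common rate and outcomes known at each look. Rule 8.7.2 is checked at every patient from 3 to 27, and 8.7.3 from patient 28. Before that the 8.7.2 limits are the tighter ones (6 against 8 at patient 14, 7 against 10 at 18–21, 8 against 13 at 22–27).

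| True rate | 8.7.2 by patient 27 | Both rules, printed, by 63 | Both rules, 20% row, by 63 | 8.7.3 alone, printed | 8.7.3 alone, 20% row |
|---|---|---|---|---|---|
| 20% | 25% | 25% | 28% | 0.6% | 16% |
| 30% | 67% | 67% | 80% | 13% | 74% |
| 35% | 83% | 83% | 94% | 34% | 92% |
| 40% | 93% | 93% | 99% | 62% | 99% |

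Reading the first toxicity cell literally as >8 changes the 8.7.3-alone printed figures by less than one percentage point.

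**4. After patient 27.** P(stop later | passed 27) = (P by 63 − P by 27) / (1 − P by 27). At a true 30%, printed row: (0.6718 − 0.6709) / (1 − 0.6709) = 0.3%. With the 20% row: (0.803 − 0.671) / (1 − 0.671) = 40%. At 35% the pair is 1.8% and 67%; at 40% it is 7.1% and 86%. At a true 20% it is below 0.1% and (0.279 − 0.251) / (1 − 0.251) = 3.7%.

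**5. Why 25% at a true 20% exceeds the 8.7.2 table.** The percentages there are single-count probabilities: exactly 3 of 6 at 20% is 20 × 0.2³ × 0.8³ = 8.2%, as printed. They are not cumulative chances of early stopping.

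**The case against.** The strongest reply is that 8.7.2 is also in force and guards the early phase tightly. That stands. A reader who looks only at 8.7.3 might infer that a clearly over-toxic treatment would usually enrol in full. The documents do not support this if both rules apply: at a true 30% or more, most trials stop by patient 27. The gain from a 20% row is then 13, 11 and 6 points at 30%, 35% and 40%, not the 61, 58 and 37 points seen for 8.7.3 alone.

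A reader might also take 25 of 63 as a likely outcome. Under both rules it needs at most 7 affected patients in the first 27 and so at least 18 in the next 36. That is permitted but unlikely.

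The 20% figures are not one quantity. In 8.7.3 it is an assumed rate, in 8.7.2 an acceptable SAE rate, and in the summary a success criterion on Grade IV GVHD and severe drug toxicity. The SAE definition in Section 11 includes hospitalization, while 11.16 lists narrower events. So 14 affected patients (14/67 = 20.9%) cannot be read as settling the success criterion, and missing that criterion is not itself a stopping rule.

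The 30% reference is an inference, and a deliberate margin above 20% is possible. The documents state no such margin.

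Other safeguards exist: termination for significant toxicity (7.1.1), continuing DSMC review (Section 11), DSMC action on raised event rates (11.15) and the DLI GVHD suspension rule (8.7.3). None is a numerical toxicity limit for all patients.

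**Conclusion.** The concern holds as an inconsistency between the 8.7.3 toxicity row and the stated 20%, and as a conflict between 8.7.2 and 8.7.3. The mismatch with 20% holds at every cut-off tried. The value of about 30% rests on an inferred flat prior and cut-off, supported by the relapse row fitting its own stated 40% under the same rule.

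The size depends on which rules apply. With both, early protection is substantial and comes almost entirely from 8.7.2; the defect is that numerical monitoring is nearly inert after patient 27. If 7.1.2 is followed literally and only 8.7.3 is used, the chance of stopping is 13%, 34% and 62% at true rates of 30%, 35% and 40%. It needs correction because a safety threshold does not match the rate the protocol states for it.

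**What to change.** 1. Reconcile 8.7.2, 8.7.3 and 7.1.2. Say which rule governs up to patient 27, cite every rule that applies, and name the event counted in each.
2. Recompute the 8.7.3 toxicity row from 20% with a stated prior and cut-off. A flat prior and 0.95 give 6, 8, 9, 11, 13, 15, 17, 18. Alternatively, if a tolerance near 30% is intended, state it and amend the 20% figures to agree.
3. Correct the first cells and bands so that patient 14 is covered.
4. Print cumulative stopping probabilities for the rules combined, at least at 20%, 30%, 35% and 40%.

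The edit is one table row and a few sentences. The statistical cost of the 20% row is more stopping when the true rate is acceptable: from 25% to about 28% at a true 20% with both rules, or from 0.6% to 16% if 8.7.3 stands alone. A higher cut-off would lower that at the price of weaker detection.

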9.0 Risks

9.1 Graft vs host disease

- Patients undergoing withdrawal of immunosuppression or DLI are at higher risk of developing severe and potentially fatal GVHD. The risk of GVHD after withdrawal of immunosuppression and DLI is 50 – 65%, and the chance of dying from it is approximately 10%.

9.2 Azacitidine risks

Primary risks of azacitidine are complications associated with hematologic toxicity such as bleeding and infection. At the dose proposed in this study, the risk of Grade III hematologic toxicity is low (<10%). Dose reduction will be used as described above for any undue toxicity encountered. A comprehensive list of side effects that have been reported with azacitidine (including cases in which the drug is given at a higher dose) is provided below:

9.2.1 Common side effects (>10%):

- **Cardiovascular:** Peripheral edema (7% to 19%), chest pain (16%), pallor (16%), pitting edema (15%)
- **Central nervous system:** Fever (30% to 52%), fatigue (13% to 36%), headache (22%), dizziness (19%), anxiety (5% to 13%), depression (12%), insomnia (9% to 11%), malaise (11%), pain (11%)
- **Dermatologic:** Bruising (19% to 31%), petechiae (11% to 24%), erythema (7% to 17%), skin lesion (15%), rash (10% to 14%), pruritus (12%)
- **Endocrine & metabolic:** Hypokalemia (6% to 13%)
- **Gastrointestinal:** Nausea (48% to 71%), vomiting (27% to 54%), diarrhea (36%), constipation (34% to 50%), anorexia (13% to 21%), weight loss (16%), abdominal pain (11% to 16%), abdominal tenderness (12%)
- **Hematologic:** Thrombocytopenia (66% to 70%; grades 3/4: 58%), anemia (51% to 70%; grades 3/4: 14%), neutropenia (32% to 66%; grades 3/4: 61%), leukopenia (18% to 48%; grades 3/4: 15%), febrile neutropenia (14% to 16%; grades 3/4: 13%), myelosuppression (nadir: days 10-17; recovery: days 28-31)
- **Local:** Injection site reactions (14% to 29%): Erythema (35% to 43%; more common with I.V. administration), pain (19% to 23%; more common with I.V. administration), bruising (5% to 14%)
- **Neuromuscular & skeletal:** Weakness (29%), rigors (26%), arthralgia (22%), limb pain (20%), back pain (19%), myalgia (16%)
- **Respiratory:** Cough (11% to 30%), dyspnea (5% to 29%), pharyngitis (20%), epistaxis (16%), nasopharyngitis (15%), upper respiratory tract infection (9% to 13%), pneumonia (11%), crackles (11%)
- **Miscellaneous:** Diaphoresis (11%)

9.2.2 Less common:

- **Cardiovascular:** Cardiac murmur (10%), hypertension (≤9%), tachycardia (9%), hypotension (7%), syncope (6%), chest wall pain (5%)
- **Central nervous system:** Lethargy (7% to 8%), hypoesthesia (5%), post-procedural pain (5%)
- **Dermatologic:** Cellulitis (8%), urticaria (6%), dry skin (5%), skin nodule (5%)
- **Gastrointestinal:** Gingival bleeding (10%), oral mucosal petechiae (8%), stomatitis (8%), weight loss (≤8%), dyspepsia (6% to 7%), hemorrhoids (7%), abdominal distension (6%), loose stools (6%), dysphagia (5%), oral hemorrhage (5%), tongue ulceration (5%)
- **Genitourinary:** Dysuria (8%), urinary tract infection (8% to 9%)
- **Hematologic:** Hematoma (9%), post procedural hemorrhage (6%)
- **Local:** Injection site reactions: Pruritus (7%), hematoma (6%), rash (6%), granuloma (5%), induration (5%), pigmentation change (5%), swelling (5%)
- **Neuromuscular & skeletal:** Muscle cramps (6%)
- **Renal:** Hematuria (≤6%)
- **Respiratory:** Rhinorrhea (10%), rales (9%), wheezing (9%), breath sounds decreased (8%), pharyngolaryngeal pain (6%), pleural effusion (6%), postnasal drip (6%), rhinitis (6%), rhonchi (6%), nasal congestion (6%), atelectasis (5%), sinusitis (5%)

- Miscellaneous: Lymphadenopathy (10%), herpes simplex (9%), night sweats (9%), transfusion reaction (7%), mouth hemorrhage (5%)

9.2.3 Rare side effects and/or case reports:

Abscess (limb, perirectal), acute febrile neutrophilic dermatosis (Sweet's syndrome), agranulocytosis, **anaphylactic shock**, atrial fibrillation, azotemia, blastomycosis, **bone marrow depression/failure**, bone pain aggravated, cardiac failure, cardiorespiratory arrest, catheter site hemorrhage, cellulitis, **cerebral hemorrhage**, CHF, cholecystectomy, cholecystitis, congestive cardiomyopathy, dehydration, diverticulitis, eye hemorrhage, fibrosis (interstitial and alveolar), **gastrointestinal hemorrhage**, glycosuria, hemoptysis, hepatic coma, hypersensitivity reaction, hypophosphatemia, infection (bacterial), injection site infection, injection site necrosis, interstitial lung disease, **intracranial hemorrhage**, leukemia cutis, reversible liver injury, lung infiltration, melena, neutropenic sepsis, orthostatic hypotension, pancytopenia, pneumonitis, polyuria, pyoderma gangrenosum, renal failure, renal tubular acidosis, seizure, respiratory distress, sepsis, septic shock, serum bicarbonate levels decreased, **serum creatinine increased**, splenomegaly, systemic inflammatory response syndrome, toxoplasmosis, tumor lysis syndrome, veno-occlusive disease of the liver.

9.3 Risk of extramedullary relapse or late relapse

Patients undergoing immunomodulatory therapy after transplant may develop extramedullary leukemia relapse despite prevention of bone marrow disease. Although their overall risk of relapse will not be increased by using immunomodulatory therapy, it is possible that this therapy will increase the tendency to relapse outside of bone marrow. In addition, previous studies have shown that patients undergoing immunotherapy may relapse later than usual (24-36 months post-transplant). While this therapy does not increase the risk of relapse overall, it is possible that immunotherapy only delays relapse in some patients.

9.4 Chimerism testing risks

9.4.1 Bone marrow aspiration

Patients will have BM exams every other cycle or about every 3 months after transplant. It is estimated that up to 6 bone marrow exams may be required in some patients. All bone marrow exams in children are done under general anesthesia, which carries a small risk (1:10,000- 1:30,000) of adverse event due to anesthesia, including death. There is universal but minor risk of local tenderness at the site of bone marrow exam, and a small risk (<1:100) of infection of the bone marrow exam site. Bone marrow biopsies are not required in this study; however, sometimes a treating physician may request a bone marrow biopsy in addition to aspirate.

9.4.2 Blood loss due to chimerism testing

Eight ml of blood or bone marrow will be obtained with each chimerism testing (3 – 12 times over the period of one year). This amount of blood is easily replaced by bone marrow production, even in a post-transplant patient. The blood will be obtained through the central line (Broviac) or with other routine blood tests.

9.5 Risk of overtreatment

In a previous analysis, approximately 30% of patients with mixed chimerism did not develop leukemia relapse, despite mixed chimerism. Unfortunately, those patients cannot be distinguished from 70% of patients who will relapse. In a more recent subset of high-risk MRD(+) patients, 7 out of 11 high-risk patients had mixed chimerism (and thus would be treated with azacitidine plus DLI on this protocol), and of those 7, 5 relapsed. Thus 2 of 7 would be “over-treated” (although these patients also received some degree of immunotherapy that may have helped prevent relapse). Patients “over-treated” on this study may be at an increased risk of developing GVHD. These patients are expected to represent a

very small minority of patients on this study, as patients with negative MRD (Standard-Risk) will not receive DLI.

10.0 Data and Safety Monitoring Plan

10.1 Oversight and monitoring plan

The UCSF Helen Diller Family Comprehensive Cancer Center (UCSF-HDFCCC) Data and Safety Monitoring Committee (DSMC) is responsible for monitoring data quality and patient safety for all UCSF-HDFCCC institutional clinical studies (see Appendix 19.6). A summary of DSMC activities for this study includes:

- Review of subject enrollment
- Review of all serious adverse events (See section 11.0)
- Monitoring every six months (depending on study accrual)
- Minimum of a yearly audit

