11.0 Adverse Events

11.1 Grading adverse events and serious adverse events

This study will use the NCI Common Terminology Criteria for Adverse Events version 4.0 (CTCAE v 4.0) found at the following website: <http://evs.nci.nih.gov/ftp1/CTCAE/About.html> for grading the severity of adverse events. The investigator is responsible for making an assessment of whether or not it is reasonable to suspect a causal relationship between the adverse event and the study treatment.

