11.12 Adverse Events Reporting

The Study Chair will assess all adverse events and determine reportability requirements to the UCSF Data and Safety Monitoring Committee (DSMC) and UCSF's Institutional Review Board, and the Committee on Human Research (CHR). Adverse events will be reported to the DSMC via OnCore.[®]

All adverse events entered into OnCore[®] will be reviewed by the Helen Diller Family Comprehensive Cancer Center Site Committee on a monthly basis. The Site Committee will review and discuss monthly the selected toxicity, the toxicity grade, and the attribution of relationship of the adverse event to the administration of the study treatment.

All grade(s) 3-5 adverse events entered into OnCore[®] will be reviewed on a monthly basis at the Site Committee meetings. The Site Committee will review and discuss the selected toxicity, the toxicity grade, and the attribution of relationship of the adverse event to the administration of the study treatment.

In addition, all suspected adverse reactions considered "serious" entered into OnCore[®], will be reviewed and monitored by the Data and Safety Monitoring Committee on an ongoing basis and discussed at DSMC meetings, which take place every six weeks.

Adverse event reporting will continue until 24 months post-transplant, or until 90 days after the patient stops trial participation, if applicable.

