11.16 SAE Reports Associated with Study Stopping Rules

The following SAEs have a potential to trigger study stopping rules (see Section 8.7) and must be reported to the Study Chair within 24 hours:

- 11.16.1 aGVHD of grade IV
- 11.16.2 Severe cGVHD
- 11.16.3 Any organ toxicity of grade IV (using CTC Common Toxicity criteria version v4.0) that is judged to be related to withdrawal of immunosuppression, azacitidine, or DLI.
- 11.16.4 Any death judged to be related to fast immunosuppression withdrawal, azacitidine, or DLI.
- 11.16.5 Note: investigators must report any aGVHD grade IV, severe cGVHD, any organ grade IV toxicity or any death in patients undergoing immunosuppression withdrawal to the Study Chair within 24 hours. Judgment about contribution of withdrawal of immunosuppression to the reported severe event will be made by DSMC within 10 days.
- 11.16.6 Phone or fax reports of SAE's due within 24 hours to:
[REDACTED]

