5.0 Proposed laboratory studies

- 5.1 Research samples will be analyzed by investigators of the National Institutes of Health intramural program. They will not be submitted for pathology review or used for diagnostic purposes rather they will be used strictly for laboratory research studies designed to characterize the levels of disease burden in patients with AML.
- 5.2 We will utilize multiple molecular biology technologies for this research including (but not limited to) microarrays, single nucleotide polymorphism arrays, gene-expression arrays using qRT-PCR, mutational arrays using qRT-PCR, digital PCR, targeted re-sequencing for common AML somatic mutations and RNA sequencing.

19.7: Multicenter Institutional Studies

Data and Safety Monitoring Plan for Multicenter Institutional Study (Phase 2 or 3 Institutional Study)

The UCSF Helen Diller Family Comprehensive Cancer Center (HDFCCC) Data and Safety Monitoring Committee (DSMC) is responsible for monitoring data quality and subject safety for all HDFCCC institutional clinical studies. A summary of DSMC activities for this study includes:

- Review of subject data
- Review of suspected adverse reactions considered “serious”
- Monthly monitoring (depending on study accrual)
- Minimum of a yearly regulatory audit

Monitoring and Reporting Guidelines

All institutional Phase 2 or 3 therapeutic studies are designated with a moderate risk assessment. The data is monitored every six months, with twenty percent of the subjects monitored (or at least three subjects if the calculated value is less than three).

The UCSF Coordinating Center provides administration, data management, and organizational support for the participating sites in the conduct of a multicenter clinical trial. The UCSF Coordinating Center will also coordinate quarterly conference calls with the participating sites to communicate the review of adverse events, safety data, and other study matters.

The Principal Investigator at the UCSF Coordinating Center will hold the role of Study Chair. The Study Chair is responsible for the overall conduct of the study and for monitoring its safety and progress at all participating sites. The Study Chair will conduct continuous review of data and subject safety and discuss each subject's treatment at monthly UCSF Site Committee meetings. The discussions are documented in the UCSF Site Committee meeting minutes.

Multicenter communication

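### The DSMC's SAE review scope is stated two ways, and sections 8.7.2 and 11.16 define the stopping-rule event differently, so attribution can enter the safety count

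*Combined protocol and SAP*

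**What the plan says.** On what the DSMC reviews:

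- Section 10.1 lists among its activities "Review of all serious adverse events (See section 11.0").
- Section 11.12, after a general sentence that adverse events go to the DSMC through OnCore, continues "In addition, all suspected adverse reactions considered" serious are reviewed by the DSMC on an ongoing basis. It also lets the Study Chair determine what is reportable to the DSMC.
- Appendix 19.7 lists "Review of suspected adverse reactions considered" serious, and repeats that scope under adverse event monitoring.
- Section 11.1: "The investigator is responsible for making an assessment of whether or not it is reasonable to suspect a causal relationship". Section 11.6 defines a suspected reaction by reasonable possibility of causation, and the table in 11.9 classes Unlikely as unrelated.

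On what the stopping rule counts:

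- Section 8.7.2: "The occurrence of any serious adverse events (SAEs) will be reported to the Coordinating Trial Center within 24 hours of learning about them", and "Accrual will stop if 3 patients with SAEs are observed in the first 3-6 patients undergoing the intervention", with limits continuing to 8 patients among 22-27. No relatedness condition is stated.
- Section 11.16 lists the SAEs that may trigger stopping: grade IV acute GVHD, severe chronic GVHD, grade IV organ toxicity judged related, and death judged related.
- Section 11.16.5 requires 24-hour reporting without an attribution filter, but for patients in whom immunosuppression is being withdrawn: "Judgment about contribution of withdrawal of immunosuppression to the reported severe event will be made by DSMC within 10 days".
- Section 11.17 gives the DSMC the judgment on azacitidine with or without DLI.

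**The concern.** The committee that is to judge relatedness has an ongoing review described as covering events already judged possibly related. After a transplant many infections, organ toxicities and deaths have a plausible alternative cause, so that first call matters. An SAE scored Unlikely by a site may not be put in front of the DSMC as an item for review.

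The stopping rule is exposed separately. Sections 8.7.1 and 8.7.2 send the reader to section 11.0, where 11.16 gives a shorter and partly relatedness-filtered list. No section says who keeps the count or which definition it uses. A count kept under 11.16 can only be equal to or lower than one kept under 8.7.2, yet both would be compared with the same limits and the same acceptable rate of 20%.

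**Working it through.** **1. DSMC scope, side by side.** Section 10.1 says all SAEs. Section 11.12 and appendix 19.7 say serious suspected reactions. The second set is the first after the investigator's causality call. These are different scopes for the same review.

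**2. What else reaches the DSMC.** Section 11.9 enters every grade 3 or higher event in OnCore regardless of attribution. Section 10.2 enters all grade 3-5 AEs and all SAEs in the trial management system. Section 11.12 reports adverse events to the DSMC via OnCore. Appendix 19.7 makes the DSMC responsible for monitoring all OnCore data from all sites. So unrelated SAEs are in data the DSMC can see. Access is less than review of each event, however: 11.12 assigns the monthly review of grade 3-5 events to the Site Committee, and 10.2 and 19.7 set data monitoring at 20% of subjects every six months.

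**3. What feeds the count.** Under 8.7.2 any SAE goes to the Coordinating Trial Center within 24 hours, and 11.14 repeats this for the sites. That stream is unfiltered and does not pass through the 11.12 review. Attribution enters only if 11.16 governs:

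| Event | 8.7.2 | 11.16 |
|---|---|---|
| Grade IV acute GVHD, severe chronic GVHD | counted if an SAE | listed, no relatedness condition |
| Grade IV organ toxicity | counted if an SAE | listed only if judged related |
| Death | counted | listed only if judged related |
| Other SAEs, e.g. hospitalization | counted | not listed |

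**4. Reach of 11.16.5.** Section 5.7.6 starts post-withdrawal azacitidine, with DLI where indicated, 2-8 weeks after withdrawal is complete. Read literally, the unfiltered note does not cover those cycles or DLI, and it asks the DSMC only about the contribution of withdrawal.

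**5. The plan's own table.** The percentages in 8.7.2 are single-look values and agree with P(X = r) to within about 0.2 points. At a 20% rate with r = 3: n = 4 gives 4 × 0.2³ × 0.8 = 2.6%, and n = 6 gives 20 × 0.2³ × 0.8³ = 8.2%, both as printed. P(X ≥ 3) would be 2.7% and 9.9%. That labelling is a separate matter. The table gives no cumulative stopping probability, so one is computed here.

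**6. Size if a filter were applied.** Inputs from 8.7.2: limits c(n) = 3 (n = 3-6), 4 (7-9), 5 (10-13), 6 (14-17), 7 (18-21), 8 (22-27). Assumed: the true per-patient SAE rate p, the fraction f of patients with SAEs left uncounted, independent patients, and a look after each patient. The counted rate is π = p(1 − f). With q(n, k) the probability of no stop through patient n with k counted:

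q(n, k) = q(n−1, k)(1 − π) + q(n−1, k−1)π for k < c(n); all mass at k ≥ c(n) stops.

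At p = 35%, π = 0.35, 0.315, 0.2625 and 0.21 for f = 0, 10%, 25% and 40%. Probability of stopping by patient 27:

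| True rate p | f = 0 | f = 10% | f = 25% | f = 40% |
|---|---|---|---|---|
| 20% | 25.1% | 18.1% | 9.9% | 4.6% |
| 35% | 83.2% | 72.6% | 51.5% | 29.0% |
| 40% | 92.9% | 85.6% | 67.1% | 41.7% |

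Starting at n = 4, as the table does, instead of n = 3, as the text does, gives the same totals.

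**The case against.** A reader might infer that the DSMC is sent only treatment-related SAEs, and that unblinded investigator attribution therefore keeps the boundary from being reached. The documents do not support that. Section 11.12 introduces the serious suspected reactions as an addition to a general adverse event feed, and sections 11.9 and 19.7 put grade 3 and higher events in data the DSMC monitors whatever their attribution. The 8.7.2 count is not drawn from the DSMC review at all. In a single-arm trial, blinded attribution was never available.

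Further points stand. Severe GVHD is largely protected: 11.16 lists grade IV acute and severe chronic GVHD without a relatedness test, 6.1 requires all GVHD in the intervention group to be reported, and 8.7.3 adds a DLI subset check with no attribution test. Section 11.17 partly fills the gap in 11.16.5, although it sets no reporting route. The table above models a filter that 11.12 and 19.7 do not apply to the count; its fractions are assumed, and the 35% and 40% rates lie outside the plan's 15-25% table.

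What remains is that 10.1 disagrees with 11.12 and 19.7, that 8.7.2 disagrees with 11.16, and that no section says which definition governs the count.

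**Conclusion.** The point holds as two inconsistencies. First, the DSMC's SAE review is stated as all SAEs and as serious suspected reactions; this needs aligning but does not itself disable the boundary. Second, the stopping rule counts any SAE in 8.7.2 while 11.16 gives a narrower list with relatedness required for grade IV organ toxicity and death, and the unfiltered note in 11.16.5 is worded only for the withdrawal period.

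If the 11.16 reading governs, sensitivity is lost in the direction of continuing. The illustration puts stopping by patient 27 at a true rate of 35% at 83% with every SAE counted, and at 73%, 52% or 29% with 10%, 25% or 40% of patients with SAEs removed. The documents give no attribution fraction, so these figures show how sensitive the rule is and do not estimate what would happen. They cover the 8.7.2 limits only; the SAE row in 8.7.3 is not modelled.

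The monthly versus six-monthly monitoring wording (10.1 against 19.7, which itself says both) is a separate minor inconsistency with no bearing on the boundary.

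**What to change.** - In 11.12 and 19.7, state that the DSMC reviews all SAEs whatever the investigator's attribution, as in 10.1.
- Widen 11.16.5 to all patients given azacitidine or DLI, with the DSMC judging the contribution of each as well as that of withdrawal.
- Reconcile 8.7.2 with 11.16 so that one event definition feeds the 8.7 count, and say who keeps it. If the any-SAE count of 8.7.2 is kept, apply no relatedness filter; basing that count on DSMC attribution would add a filter 8.7.2 does not have. If the 11.16 list is used, count each event until the DSMC, not the investigator, rules it unrelated, and restate the acceptable rate and the 8.7.2 table for that event.
- Separately, give one monitoring frequency in 10.1 and 19.7.

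The cost is protocol wording and some additional SAE reports for the existing DSMC to read. Those reports must already reach UCSF within 24 hours under 8.7.2 and 11.14. Choosing the 11.16 list also means recalculating the table.
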